### **5.3.2.2 Prospective skin arm (See 12.11)**

In addition to those patients experiencing skin toxicity and recruited at the time of toxicity, patients who are due to be commenced on a oncological treatment will be recruited to a prospective observational cohort study. They will be provided Prospective Punch Biopsy Patient Information Sheet. All visits and procedures shall take place either in out-patient Dermatology or Oncology

Protocol V17 07.02.2023

Clinics at experienced centres or established Clinical Research Units (CRU). Patients will be seen on two occasions by a trained health professional.

**Visit 1:** A representative 6mm punch biopsy will be taken from the patient's skin prior to treatment commencing. Furthermore, patients may also have a paired blood sample (up to 50mls) and plucked hair follicles (up to 20) taken.

**Visit 2:** A second review will be made within the first 4 weeks after treatment has been commenced at which point patients will be reviewed and a full skin examination performed. Patients will be grouped into those who develop skin reactions and those who do not. In those patients who develop a skin reaction, a 6mm punch biopsy will be taken from the affected skin in addition to a 6mm punch biopsy of the adjacent non-affected skin. If patients wish only to give a single punch biopsy then this will be taken from the involved skin. In patients who do not develop a skin reaction, a 6mm punch biopsy will be taken from a representative area of skin. In those patients who develop reactions involving the scalp we will ask the patient if they would be willing to have two smaller punch biopsies (up to 5mm) taken from the scalp in addition to normal skin (as above). In addition, 40mls of blood and up to 20 plucked hair follicles may be collected.

Should a patient develop a skin reaction subsequent to their follow up visit they will be offered the opportunity for a further skin biopsy (with paired blood sampling). As with the recruitment of patients at the point of toxicity a subsequent sample (with a paired blood sample) may be taken at the point of resolution.

At all points in skin sampling patients may be asked to complete a 5 minute questionnaire to assess the impact of their skin on their quality of life. This assessment is known as the Dermatology Life Quality Index Questionnaire (DLQI) and is a validated questionnaire used regularly in dermatology outpatient clinics. Clinical photographs may be taken at each time point.

### **5.3.2.3 Biopsy procedure**

After the procedure patients will require 1 or 2 sutures, removable after 7 days for the arms, 10 days for the legs and 14 days for the back. We will arrange a follow up visit to remove the sutures; removal of sutures shall take place at the CRU RLBUHT or at dermatology out-patients departments. The risks associated with punch biopsies are considered very small and may include bleeding, infection and small scarring. Although the risks are considered small and treated simply, participants will be advised to visit their General Practitioner (GP) if concerned. If a participant consents to the biopsy procedure as part of the study, a letter will be sent to the GP with notification of their participation. The biopsies and plucked hair follicles may be processed in a number of ways depending on the intended investigations planned. Therefore, samples will be either snap frozen in liquid nitrogen and immediately stored at -80°C, fixed in formaldehyde for paraffin embedding (FFPE), stored in RNAlater® (Qiagen, Manchester, UK) to preserve RNA integrity, or kept as fresh samples in transport media to either be processed fresh or slow frozen.

### **5.3.3 Thyroid Biopsy**

Whilst irAEs can manifest in almost any organ CPI-associated endocrinopathies are irreversible and thus of particular interest. Endocrine irAEs include hypophysitis, hypopituitarism, hypoadrenalism, thyroiditis and new onset type 1 diabetes mellitus. Whilst thyroid irAE (TirAEs) were only seen in a small minority of patients treated with ipilimumab (4%) the incidence is 6-11% in patients treated with PD-1 inhibitors, nivolumab and pembrolizumab. When CPIs are used in combination the TirAE incidence is increased further with the Checkmate 067 trial reporting an incidence of 15%.

Protocol V17 07.02.2023

This figure has consistent across subsequent combination trials irrespective of CTLA-4 dosing.

Whilst it is broadly accepted that the mechanism of CPI-induced TirAEs is immune in origin further characterisation of the underlying mechanisms within the immune setting is required.

Drug induced thyroiditis is caused by relatively few drugs and even fewer cause toxicity by an immune mediated mechanism. Characterization of the histopathological, cellular and transcriptomic features of TirAEs is an entirely novel area of research. Undertaking FNAs to acquire thyroid material and associated immune cells is likely to greatly inform mechanistic understanding of the events and potential mechanisms of TirAEs. In addition to this the knowledge and understanding of TirAEs will convey insight into mechanisms in more complex organ systems and thus CPI irAEs as a group.

Fine needle aspiration (FNA) of the thyroid gland in patients experiencing TirAEs will be undertaken by experience interventional radiologists under image guidance. Samples will be taken following the commencement of thyroid dysfunction for research purposes. A single lobe, double pass technique will be undertaken to ensure that sufficient cellular material gained whilst maintaining patient comfort. The use of local anaesthetic will be utilised where indicated. There are minimal risks of FNA investigation. Side effects may include a small area of bruising. Risk of infection is minimised by the use of aseptic conditions. The use of image guidance minimises the risk of any additional effects.

A paired blood sample (50mls) will be taken alongside the FNA sample. Analysis utilising cytometry techniques, other forms of cellular/ cytokine analysis, transcriptomics and additional protein or gene analysis will be undertaken to characterise CPI TirAEs including potential mechanism. If patients do not wish to give a thyroid biopsy then a single blood test can also be taken as part of this study arm.

### **5.3.4 Liver Biopsy**

Standard toxicological studies during the preclinical phase of drug development do not reliably detect potential hepatotoxicity of novel agents. Hepatotoxicity has been the 2nd most common reason for withdrawals worldwide, accounting for 32% of 47 such drug withdrawals in 3 decades. Lack of specific tests means that the diagnosis of drug induced liver injury (DILI) is often delayed or left unrecognised. In a recent prospective population-based study, the annual incidence of DILI was 19 per 100,000, of which 23% are hospitalised and 1% died. Mortality from liver failure among DILI patients who present with jaundice is approximately 10%. Hepatotoxicity from chemotherapy and other systemic anticancer therapies occurs commonly and in an unpredictable or idiosyncratic fashion. CPIs are also associated with unpredictable hepatotoxicity affecting 7-33% of patients across all grades. The mechanisms of toxicity are varied and currently largely unclear. It is well known that tissue biopsy and histological analysis are essential in fully understanding the pathological processes occurring and thus necessary to gain a complete understanding of toxicity. This is particularly the case in drug classes where animal models are unable to provide insight due to complex immunological differences between species such as the case with CPIs.

Radiologically guided biopsy of the liver will be undertaken in patients who have clinically significant drug induced hepatotoxicity (CTCAE Grade 3 or 4 and/or high risk clinical phenotype or toxicity behavior eg those with pre-existing liver disease or patients with atypical blood test derangement which are not captured by the currently used CTCAE criteria) whom are considered low risk (INR <1.5 and Platelets >150). Upto 2 cores of liver tissue (upto 25mm in length) will be taken at biopsy. In low risk patients having a non-targeted liver biopsy carries low risk of complications associated with the

Protocol V17 07.02.2023

procedure (<0.1%; <1 in 1000^36). Samples will be either fixed in formaldehyde for paraffin embedding (FFPE), stored in RNeasy Lysis Buffer (Quiagen, Manchester, UK) to preserve RNA integrity, or kept as fresh samples in transport media to either be processed fresh or slow frozen.

A paired blood sample (50mls) and urine sample (25mls) will be taken alongside the tissue sample. The urine will be frozen and/or freeze dried. Analysis utilising cytometry techniques, other forms of cellular/ cytokine analysis, transcriptomics and additional protein or gene analysis will be undertaken to characterise hepatotoxicity including potential pathological mechanisms. Alongside liver biopsy and blood/urine sampling a liver stiffness assessment will be undertaken. This is a non-invasive ultrasound based modality which carries no procedural risk.

If patients do not wish to give a liver biopsy then a single blood +/- urine +/- stiffness test can also be taken as part of this study arm.

#### **5.4 Sample Storage and Data Collection**

Samples will be processed at the relevant institution with the necessary facilities and regulatory approvals in place and then transferred/delivered to the University of Liverpool, Department of Pharmacology Laboratories. We have implemented a new bar coding system in the Department which adds further security in terms of sample tracking and also for confidentiality purposes. All biological samples stored within the Department are in keeping with the Human Tissue Act (license held by the University of Liverpool).

Representative data to be collected will include diagnosis of ADR, symptomatic presentation and type of drugs involved as defined above. Age, weight, height, ethnicity (in the form of a questionnaire), medical history, concomitant medication at time of reaction, current medication, and if available, clinical blood sample and investigational results conducted at time of reaction will also be collected (**Appendix 5**). The patient's clinical care will not be affected in any way by taking part in the study.

### **6. Safety Assessment**

The study will be conducted with close attention to patient safety. Participants recruited will have their blood sampled by venepuncture. Donating blood by venepuncture produces minimal risk of bruising or bleeding. This procedure will be carried out by trained, competent health professionals.

### **7. Direct Access to Source Data and Documents**

The Case Record Forms (CRFs) will be supplied by the Investigator for recording all data collected during the study. All CRFs are to be completely filled out by personnel administering the study procedures and once final review has been conducted and signed by the Chief Investigator or nominated designee. All CRFs are to be completed in a clear, legible manner. Black ink must be used to ensure accurate interpretation of data. Any changes or corrections made by drawing a line through the data to be changed, entering corrected information, and signing (or initialling) and dating the change. Erasing, overwriting, or use of "liquid paper" is not permitted on CRFs.

Protocol V17 07.02.2023

As this study will be recruiting patients from a wide variety of sources, once the CRF is returned to the University and entered onto a specially designed database, the CRF may then also be classed as the source documentation. Data collected into the CRF's and subsequently entered onto the database will be reviewed for discrepancies, missing data and queries. Research nurses and data managers will liaise with the relevant clinicians regarding data corrections. The Chief Investigator will be updated on a regular basis and will review the reports produced by the statistician in order to ensure consistency and accuracy of the data. Once CRF's and corresponding queries and reports are reviewed, the CRF will be signed off by the Chief Investigator or designated person.

The database especially designed for this project will be held at the University of Liverpool in the Department of Pharmacology and Therapeutics Research Office. It will be password protected and is backed up on a daily basis.

The following abbreviations are for use when values or answers cannot be provided: NA = Not Applicable, NK = Not Known, ND = Not Done, NR= Not Retrievable or Not Available.

Every effort should be made to have the CRFs completed and as soon as possible following a subject's study visit.

All study documentation, as defined above will also be made available to the Ethics Committee and to regulatory authorities for inspection on request.

Individual subject medical information obtained as a result of this study is considered confidential and disclosure to third parties other than those noted below is prohibited. Records identifying the subject will be kept confidential and, to the extent permitted by the applicable laws and/or regulations will not be made publicly available. All study centre personnel will comply with the privacy rules of their institutions and /or professional groups and with the ICH Guideline for Good Clinical Practice.

Individual subject medical information obtained as a result of this study is considered confidential and disclosure to third parties is prohibited, except for inspection on request by one or more of the following:

- The Research Ethics Committee
- Auditors (including those instructed by regulatory bodies)

Documents relating to the trial that contain personal data that may disclose the identity of the subject should remain with the Investigator in a locked filing cabinet. The Investigator should not provide any personal data that may identify the subject to any third party at any time during or after the study. Subject confidentiality will be further assured by utilising unique subject identification code number. The link between the patient's name and code will be broken and the sample completely anonymised when the study is completed and all clinical data have been obtained.

The Investigator must maintain adequate records for the study including completed CRFs, volunteer medical records, laboratory reports, worksheets, nursing notes, signed Consent Form/Subject Information Sheet, drug disposition records, adverse experience reports, information regarding

Page **28** of **46**

Protocol V17 07.02.2023

subjects who discontinued, all correspondence with the Research Ethics Committee and other pertinent data.

All records are to be retained by the Investigator for the period of 15 years.

## **8. Ethics**

Potential subjects for the study will have been identified by one of the sources of recruitment highlighted in section 4. The majority of potential subjects will be given a detailed oral presentation of the study nature and receive detailed written information. All subjects will be informed of the nature and purpose of the study, its requirements and possible hazards, and their rights to withdraw at any time from the study without prejudice and without jeopardy to any future medical care at the study site. They will have adequate opportunity to ask the Investigator or nominated designee about any aspect of the study. Each subject must agree to co-operate in all aspects of the study and must be given informed written consent to the Investigator for participation.

Three Consent Forms will be signed, one for the researcher, one for the casenotes and the other for the participant. Signed Consent Forms must remain in the study file and be available for monitoring purposes at any time.

The study will be conducted in compliance with the guidelines of the Declaration of Helsinki on biomedical research involving human volunteers (Hong Kong revision, 1989 and the 48th General Assembly, Somerset West, Republic of South Africa, October 1996, updated in October 2000), ICH-GCP guidelines, relevant regulatory guidelines, and the study protocol. The protocol and relevant substantive data will be submitted for consideration by the Local Research Ethics Committee and written approval from the Chair of the Ethics Committee is required before the study is initiated and clinical activities of the study can commence.

The Ethics Committee will be notified promptly by the Investigator of the following:

- a) Deviations from, or changes of, the protocol to eliminate immediate hazards to the trial volunteers.
- b) Changes increasing the risk to volunteers and/or affecting significantly the conduct of the trial.
- c) New information that may affect adversely the safety of the volunteers or the conduct of the trial.
- d) As the research consists of blood sample and data collection only, there will be no adverse event reporting. However for safety reasons, if a problem occurs during or following venepuncture when collecting a blood sample, this will be recorded in the CRF. Although the risks associated with this intervention are minimal and occur very rarely.

Any major changes to the protocol will be made by means of a formal written protocol amendment and submitted for approval by the Research Ethics Committee. The Committee will also be kept informed of study progress and will receive a copy of the final study report.

Protocol V17 07.02.2023

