#### **4.2.5 *Co-enrolment Guidelines***

Patients registered for the Hypersensitivity study are not restricted to entry onto any other clinical trial, study or research project as this study consists of blood sampling. However information regarding any trial participation will be collected on the follow-up CRF forms.

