#### **5.3.1 Colonic Biopsy**

Collection of colonic tissue samples is considered standard of care for diagnostic purposes in the case of colitis and forms part of the clinical care algorithm for CPI induced colitis. Sampling for this study would occur during a clinically indicated endoscopy but we would request a further biopsy samples (up to 12 in number) to be taken for research purposes. This will allow comprehensive sampling, even if the inflammation is patchy. These would be placed in either in cell medium and processed fresh or appropriate freezing media with a view to future work using cytometry techniques and other forms of cellular/ cytokine analysis or analysis of bacteria or proteins or genes. Additionally a request for permission to retrieve the clinical blocks after clinically indicated analyses have been performed will be made and histopathological/ immunohistochemical analysis performed. The patients will also have a paired bloods sample taken (50mls) at the time of endoscopy. **NO** endoscopic procedures would be undertaken for research purposes alone.

There may be some minor but short-lasting discomfort from having a blood test. Patients will not feel the biopsies being taken. There is a very small risk of complications (such as bleeding or perforation) from having any biopsy of the bowel, but it is important to note that the biopsy will be taken by an experienced endoscopist and will be done at sites with extensive endoscopic experience with established clinical practice. If patients have experienced colitis but are unable to give endoscopy samples a single (upto 50mls) blood sample can be given as part of the colitis substudy.

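### Section 8(d) waives adverse event reporting because the study only takes blood and data, but Section 5.3 adds colonic, skin, thyroid and liver sampling with no defined route for recording its harms

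*Protocol*

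**What the plan says.** Section 8 lists what the ethics committee is to be told promptly. Item (d) of that list is a waiver: "As the research consists of blood sample and data collection only, there will be no adverse event reporting". It makes one exception: "if a problem occurs during or following venepuncture when collecting a blood sample, this will be recorded in the CRF".

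Section 6, the whole of the safety assessment, has the same scope: "Participants recruited will have their blood sampled by venepuncture" and "Donating blood by venepuncture produces minimal risk of bruising or bleeding". It mentions no other procedure. Section 4.2.5 justifies unrestricted co-enrolment "as this study consists of blood sampling".

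Section 5.3 describes a different study:

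- **Colon (5.3.1).** Up to 12 further biopsies for research, taken at an endoscopy that must itself be clinically indicated. The section concedes: "There is a very small risk of complications (such as bleeding or perforation) from having any biopsy of the bowel".
- **Skin (5.3.2 to 5.3.2.3).** Punch biopsies of up to 6 mm, closed with sutures. The stated risks are bleeding, infection and scarring.
- **Thyroid (5.3.3).** An image-guided, double-pass aspiration: "Samples will be taken following the commencement of thyroid dysfunction for research purposes". Bruising is named as a side effect.
- **Liver (5.3.4).** "Radiologically guided biopsy of the liver will be undertaken in patients who have clinically significant drug induced hepatotoxicity", with up to two cores. The complication risk is given as below 0.1% in low-risk patients, citing a national audit.

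**The concern.** The waiver is a stated rule with a stated reason, and the reason is untrue of the protocol that contains it. Sections 4.2.5, 6 and 8(d) describe a blood-sampling study and do not match the tissue arms in Section 5.3.

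At stake is the safety of people who accept invasive sampling for research. A site that follows Section 8(d) has an instruction for a bruise after venepuncture. It has none for a bleed after a liver core or a perforation after extra colonic sampling. Without a defined route, whether such an event reaches the investigator or the ethics committee depends on local practice, and no count per procedure can be relied on.

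**Working it through.** No arithmetic applies. The protocol states no figure that depends on this rule, so the check is a comparison of sections.

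**Step 1: is the premise true?** Section 8(d) rests on the research being limited to blood and data. Section 5.3 contains four kinds of tissue sampling. The colonic, skin and thyroid samples are expressly for research. Section 5.3.4 does not use that phrase for the liver biopsy, but it lets a patient decline the biopsy and stay in the arm with blood, urine or a stiffness test. That marks the biopsy as an optional study procedure. The premise is false.

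**Step 2: what is recorded for each procedure?**

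| Procedure | Harm named in the protocol | Recording rule | Stated post-procedure contact |
|---|---|---|---|
| Venepuncture | Bruising, bleeding (6) | CRF (8(d)) | None specific |
| Skin punch | Bleeding, infection, scarring (5.3.2.3) | None | Suture removal (5.3.2.3) |
| Thyroid aspiration | Bruising; infection risk described as minimised (5.3.3) | None | None |
| Extra colonic biopsies | Bleeding, perforation (5.3.1) | None | None |
| Liver biopsy | Complications below 0.1% (5.3.4) | None | None |

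One of the five procedures has a recording rule, and it is the least invasive.

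**Step 3: is there a route elsewhere?** Four other places were checked.

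- Appendix 7, the CRF content list, has biopsy only as a clinical or investigational result. It has no item for procedure complications.
- Section 5.3.2.3 advises participants with concerns after a punch biopsy to see their GP. The GP is told of participation, but no report back to the study is described.
- Section 7 includes reports of adverse experiences in a general list of records to keep. It does not say who generates them or when.
- Section 8(c) requires prompt notification of new information bearing on volunteers' safety. It does not say how individual events would be collected.

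None of these sets up collection of events after a biopsy or aspiration.

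**Step 4: could existing visits serve?** Suture removal is a natural point for skin. Appendix 3 has later blood visits for oncology cases, but it allows the schedule to be cut to a single sample and ties no visit to biopsy follow-up. Appendix 2 gives other patients a recall visit without a fixed time.

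**The case against.** The strongest reply is that item (d) waives reporting and does not forbid recording. Section 7 requires medical records, nursing notes and reports of adverse experiences to be kept. Section 8(c) imposes a general duty to notify. Section 11 gives a monitor the task of seeing that patient safety is not compromised, and the study is bound to ICH-GCP and to local policies that are not shown. A serious bleed would very probably appear in clinical notes.

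Much of this stands. A reader might infer that no biopsy harm would ever be recorded, or that the ethics committee could never learn of one. The documents do not support that, because these provisions leave several ways for an event to surface. What they do not do is define a route, and Section 8(d) points the other way.

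The reply is also right to separate the research increment from clinical care. The colonic endoscopy is clinically indicated, so only the extra biopsies add research risk. Section 4.2.5 is a co-enrolment statement and not a safety rule; it matters only because it repeats the outdated description.

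**Conclusion.** The contradiction is real and should be corrected. Section 8(d) gives a false reason for having no adverse event reporting, Section 6 omits the invasive procedures, and four kinds of tissue sampling have no defined route for recording or reporting their harms. This rests on the current text alone, together with reading the liver biopsy as a study procedure because patients may decline it.

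No numerical size is offered. A reader might combine the liver figure with 100 biopsies to quote a chance of at least one complication, or an upper bound if none were seen. The protocol supports neither. The 100 in Sections 2.2 and 3.6 is a target or cap on cases per drug or reaction, and no number of liver biopsies is stated. The 0.1% is a ceiling taken from an outside audit, not a rate. Nor is estimating complication rates an aim or endpoint of this study, so the absence of such an estimate is not the fault. The fault is the missing route.

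**What to change.** 1. In Section 8(d), delete the description of the research as blood and data only, and delete the waiver that depends on it.
2. Extend Section 6 to every procedure in Section 5.3, and correct the description in Section 4.2.5.
3. Require problems during or after any study sampling procedure (liver, thyroid, colonic, skin and venepuncture) to be recorded in the CRF, and add an item for this to Appendix 7.
4. Require related serious events to be reported promptly to the sponsor and the ethics committee.
5. Give counts of procedures and of problems, by procedure, in the annual report to the ethics committee already planned in Sections 3.6 and 4.2.1.
6. State when events are captured. For skin, use the suture-removal visit. For liver, thyroid and colon, name a later sampling visit that is already scheduled, or a check of the clinical record where no such visit takes place.

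The cost is a protocol amendment, a CRF item and some added data collection, mostly for liver, thyroid and colon, where no post-procedure contact is stated. No sampling procedure or clinical rule needs to change.
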